List of abb	reviations
AE	Adverse event
AESI	Adverse Event of Special Interest
ALP	Alkaline Phosphate
ALT	Alanine Aminotransferase
ARR	Annualized Relapse Rate
AST	Aspartate Aminotransferase
ATC	Anatomical Therapeutic Classification
BMI	Body Mass Index
C-CASA	Columbia Classification Algorithm for Suicide Assessment
CCD	Confirmed Cognitive Decline
CDW	Confirmed Disability Worsening
CRF	Case Report/Record Form (paper or electronic)
CRO	Contract Research Organization
eCRF	Electronic Case Report Form
eCRS	Case Retrieval Sheet
CSR	Clinical Study report
CTC	Common Toxicity Criteria
CTCAE	Common Terminology Criteria for Adverse Events
CTSD	Clinical Trial Safety Disclosure
DBP	Diastolic Blood Pressure
DMF	Dimethyl Fumarate
CCI	
DMT	Disease Modifying Treatment
DRF	Diroximel Fumarate
eCSSRS	(electronic) Columbia Suicide Severity Rating Scale
ECG	Electrocardiogram
EDSS	Expanded Disability Status Scale
EMA	European Medicines Agency
EOS	End of Study
FAS	Full Analysis Set
FDA	Food and Drug Administration
FS	Functional Score
CCI	
FU	Follow-up
Gd	Gadolinium
CCI	
9HPT	9-Hole Peg Test
CCI	Head Date
HR	Heart Rate
lgG	Immunoglobulin G
IgM	Immunoglobulin M
CCI IDD	Injustion related reaction
IRR	Injection related reaction
KM LC)/A	Kaplan-Meier
LCVA	Low Contrast Visual Acuity

LFT Liver Function Test
LLN Lower Limit of Normal

M Month

MedDRA Medical Dictionary for Drug Regulatory Affairs

MH Medical History

MMRM Mixed Model for Repeated Measures

MRI Magnetic Resonance Image

MS Multiple Sclerosis

CCI

NB

Negative Binomial

NEDA No evidence of disease activity

NfL Neurofilament

PD Pharmacodynamics/Protocol Deviation
PDS Programming Dataset Specification

PK Pharmacokinetics
PR Pulse Rate

PRO Patient-reported Outcomes
PSDS Post Study Drug Supply

PT Preferred Term
PTA Post-Trial Access

RMS Relapsing Multiple Sclerosis

CCI

RRMS Relapsing-Remitting MS
SAE Serious Adverse Events
SAF Safety Analysis set
SAP Statistical Analysis Plan
SAS Statistical Analysis Software
SBP Systolic Blood Pressure

CCI

s.c. Subcutaneous

CCI

SFU Safety Follow-up
SIB Self-Injurious Behavior
SOC System Organ Class
SPMS Secondary progressive MS
TEAE Treatment Emergent AE
T25FW Timed 25-foot Walk
TBIL Total Bilirubin

CCI

ULN Upper Limit of Normal

CCI

WHO World Health Organization

1 Introduction

The purpose of this statistical analysis plan (SAP) is to describe the implementation of the statistical analysis planned in the protocol of study COMB157G23101.

The content of this SAP is based on protocol OMB157G23101 version 03.

[figure not shown]
Data will be analyzed by Novartis or a contracted contract research organization (CRO) according to the data analysis section 12 of the study protocol. Important information is given in the following sections and details will be provided, as applicable, in Appendix 16.1.9 of the CSR.

1.1 Study design

This is a single arm, prospective, multicentre and open-label, 96-week study to evaluate the treatment effectiveness of ofatumumab (OMB157) in subjects with relapsing MS transitioning from any fumarate-based RMS approved therapy, such as DMF or DRF, or fingolimod due to breakthrough disease activity. A total of approximately 555 eligible subjects will receive open-label ofatumumab 20 mg s.c. every 4 weeks (after an initial loading regimen of three weekly 20 mg doses in the first 14 days).

The study is divided into three parts: Part 1 - Screening period, Part 2 - Treatment period, Part 3 - Safety follow-up.

Figure 1-1 Study Design

Transition period is described in protocol Section 6.6.1.

Part 1 - Screening (and transition) period

The Screening period can last up to 60 days and consists of two sections; namely Screening section and Baseline section. The Screening period will include the transition period (see

protocol Section 6.6.1 for details around subjects transitioning from either a fumarate therapy or fingolimod as per clinical practice). Baseline section can last up to the point of first study drug administration (Day -7 to Day 1). Participant eligibility will be determined based on the Screening and Baseline assessments.

Part 2 - Treatment period

Treatment period will consist of an initial induction phase (Week 1 to Week 4) with 20 mg s.c. of atumumab during visits at Day 1, Day 7 and Day 14 followed by a monthly maintenance dose regimen of 20 mg s.c. of atumumab every 4 weeks starting at Week 4. During the treatment period, the subjects will have the assessments as per Table 8-1 in the protocol. All visits should be performed in the morning whenever possible to reduce the impact of fatigue on the scheduled assessments.

Part 3 - Safety follow-up period

Safety follow-up:

- The Safety follow-up (FU) period will be applicable for the following subjects:
 - Subjects who complete the Treatment period on the study drug and do not continue ofatumumab treatment (either commercial ofatumumab via prescription or via Post-Trial Access mechanisms*)
 - Subjects who prematurely discontinue study drug
- All Safety FU visits must be scheduled relative to the End of Study (EOS) Visit.

*Post-Trial Access

In the countries where of atumumab is not approved by Health Authorities, not launched or reimbursed, subjects participating in the current study with a clinical benefit in the opinion of the Investigator at the completion of the Treatment period may continue to receive of a tumumab via a Post-Trial Access (PTA) mechanism until ofatumumab becomes commercially available and it is reimbursed in the particular country or until the PTA program ends, whichever occurs first. Reimbursement refers to country level and not individual reimbursement, if there are multiple reimbursement channels in a country the date of reimbursement is when the first major reimbursement is in place. Post Study Drug Supply (PSDS) is the first option for PTA. If PSDS cannot be implemented in a country due to the local legislation, the clinical trial team will work with the Investigator to assess other PTA possibilities.

All participants continuing of atumumab after the study completion (either commercial ofatumumab via prescription or via Post-Trial Access mechanisms), must complete the EOS visit of this study first.

1.2 Study objectives and endpoints

Table 1-1 Objectives and Endpoints

Objective(s)	Endpoint(s)		
Primary objective(s)	Endpoint(s) for primary objective(s)		
Demonstrate the effectiveness of ofatumumab 20 mg s.c. administered every 4 weeks in subjects with relapsing forms of MS who had breakthrough disease on fumarates or fingolimod	Annual relapse rate (ARR, based on confirmed relapses) measured over the 96 weeks		
Secondary objective(s)	Endpoint(s) for secondary objective(s)		
Evaluate the safety of ofatumumab 20 mg s.c. administrated every 4 weeks in subjects with relapsing forms of MS who had breakthrough disease on fumarates or fingolimod	 Proportion of subjects with adverse events, including injection related reactions Proportion of subjects with laboratory or vital signs results meeting abnormal criteria The proportion of subjects discontinuing treatment due to insufficient effectiveness (lack of efficacy) or tolerability/safety reasons 		
Exploratory objective(s)	Endpoint(s) for exploratory objective(s)		
Demonstrate effectiveness of ofatumumab 20 mg s.c. administered every 4 weeks	 Change from Baseline during the treatment period, of the following Assessments: EDSS Timed 25-Foot Walk (T25FW) Nine-Hole Peg Test (9HPT) Low Contrast Visual Acuity (LCVA) T2 lesion volume Time to 6-month Confirmed Disability Worsening (6mCDW) based on EDSS Time to a 6-month confirmed cognitive decline (6mCCD), defined as a 4-point worsening on Number of T1 Gd+ lesions per scan Number of new or enlarging T2 lesions on MRI per year (annualized T2 lesion rate) Proportion of patients without MRI activity Proportion of subjects with No Evidence of Disease Activity (NEDA-3) as per protocol defined events during a 96-week period 		
Explore patient reported outcomes in subjects treated with ofatumumab 20 mg s.c. administered every 4 weeks	Change from Baseline during the treatment period of the following Assessments: The impact of MS disease as measured by the CCI CCI CCI CCI CCI CCI CCI CCI		
Explore Neurofilament (NfL) light chain as a biomarker for MS in terms of prognosis and disease activity monitoring	Change from baseline in serum NfL light chain concentration		

Objective(s)	Endpoint(s)			
• Explore the utility of using the application	Adherence to Classessments quantified as compliance level (%), which will be measured in terms of Classessments and other assessments performed in the study CCI includes the following: CCI CCI CCI CCI CCI CCI CCI C			
Explore daily activity and sleep patterns via	Change from Baseline in CCI derived metrics			

[figure not shown]
2 Statistical methods

2.1 Data analysis general information

Novartis statistical and programming team will be performing the final CSR analysis unless otherwise specified. The Statistical Analysis System (SAS) 9.4 and/or R 3.6.1 or higher versions will be used.

Unless otherwise stated, summary tables/figures/listings will be on all subjects in the respective analysis sets. Categorical data will be presented as frequencies and percentages. For continuous data, mean, standard deviations, median, 25th and 75th percentiles (optional), minimum and maximum will be presented.

For efficacy analyses on the full-analysis set (FAS), all available data collected in the database

2.1.1 General definitions

Below some general definitions to be used in the rest of the document are summarized.

Table 2-1 General Definitions

Table 2-1 General Deminitions	
Study treatment/Study drug	The investigational drug (ofatumumab) will be referred as study treatment or study drug.
Date of first administration of study drug/first dose date	The first dose date of active study drug administration.
Date of last administration of study drug/last dose date	The last dose date of active study drug administration.
Study Day 1 or Day 1	The date of first administration of study drug/first dose date.
Study Day	 All other study days will be labeled relative to Day 1. For events with dates on or after Day 1, study day for the event is calculated as (event start date – first dose date + 1). For events with dates before Day 1, study day for the event is calculated as (event start date – first dose date). Day 0 will not be used.
Duration of an event	Duration of an event is calculated as (event end date – event start date +1).
1 month	30 days; to be used in defining 6-month confirmed disability worsening or improvement.
4 weeks	28 days; to be used in determining target days of scheduled visits. It is based on the scheduled injection frequency for ofatumumab (during the maintenance phase).
Day post-study drug discontinuation	Day post-study drug discontinuation for a particular event is calculated as (event start date – study drug discontinuation date).
Baseline	Baseline is the last assessment obtained prior to the first administration of study drug. No visit windows will be needed for the identification of baseline assessment.
	For pulse and blood pressure vital sign values, the baseline is the average of the non-missing values of the 3 measurements taken on the last visit prior to the first administration of study drug. The pre-injection assessment values on Day 1 vital sign case report form (CRF) page will not be used for baseline derivations.

On-treatment period	On-treatment period includes days from the first injection date until 30 days after the last injection date. This definition considers subjects on ofatumumab are scheduled to inject every 28 +/- 3 days. For calculation of compliance to study drug administration, similar definition of on-treatment period will be used.

2.1.2 Visit Windows

2.1.2.1 Visit windows for treatment epoch

Visit-windows will be used for both efficacy and safety data summaries by visit. Visit windows define a time period "around" the targeted visit date as defined in the evaluation schedule of the clinical study protocol. Visit-windows are non-overlapping, and defined without gaps between consecutive visit windows. The width of visit windows may vary over the course of the study period.

Baseline assessments are defined in Section 2.1.1 and do not require a visit window.

The purpose of visit windows is to analyze data based on the actual study days (rather than "nominal" visits). E.g., if a subject's Month 1 visit is delayed; it is possible that the Month 1 data be re-aligned to visit-window Month 2 and be summarized under Month 2.

- For efficacy analyses all nominal visits (i.e. excluding unscheduled visits) will be mapped into one of the defined visit-windows. Note: for the derivation of disability worsening or improvement all visits (scheduled and unscheduled) need to be considered before the worsening or improvement can be confirmed. Similarly, for No Evidence of Disease Activity (NEDA-3), all visits (scheduled and unscheduled) need to be considered.
- For safety analyses all visits (scheduled and unscheduled) will be mapped to visit windows. Safety data from unscheduled visits may be reported separately if applicable.

It is possible that more than one assessment of a subject fall into a particular visit-window. Section 2.1.2.3 deals with the statistical approaches to handle multiple visits in a given visit window.

Tables displaying summary statistics "by visit" will also use the term visit-window as column header; this is to remind the reviewer that multiple assessments of a participant might be summarized. Below tables provide visit-windows definitions for applicable parameters.

Table 2-3 Visit-windows for EDSS / T25FW / 9HPT

Visit-window	Start day	Target day	End day
Week 24	1	168	252
Week 48	253	336	420
Week 72	421	504	588
Week 96	589	672	762

Table 2-4 MRI

Visit-window	Start day	Target day	End day
Week 24	2	168	252
Week 48	253	336	504
Week 96	505	672	762

Table 2-5 Visit-windows for vital signs*

		 			
Visit-window	Start day	Target day	End day		
Week 4	1	28	98		
Week 24	99	168	252		
Week 48	253	336	420		
Week 72	421	504	588		
Week 96	589	672	762		

^{*} Data collected from Day 1 protocol scheduled visit will not be mapped to the visit windows due to different data collection on this visit.

Table 2-6 Visit-windows for routine laboratory values

Visit-window	Start day	Target day	End day
Week 4	1	28	56
Week 12	57	84	126

Week 24	127	168	252
Week 48	253	336	420
Week 72	421	504	588
Week 96	589	672	762

Table 2-7 Visit-windows for B-cell counts, IgG levels, IgM levels, PROs*

Visit-window	Start day	Target day	End day
Week 4	1	28	98
Week 24	99	168	252
Week 48	253	336	420
Week 72	421	504	588
Week 96	589	672	762

^{*}Patient Reported Outcomes include CCI

Table 2-8 CCI LCVA, CCI

Visit-window	Start day	Target day	End day
CCI			504
Week 96	505	CCI	762

Table 2-9 Visit-windows for biomarker data

Visit-window	Start day	Target day	End day
Week 4	1	28	56
Week 12	57	84	126
Week 24	127	168	210
Week 36	211	252	294
Week 48	295	336	378
Week 60	379	420	462
Week 72	463	504	546
Week 84	547	588	630
Week 96	631	672	762

Table 2-10 Visit-windows for eCSSRS

Visit-window	Start day	Target day	End day
Week 2	1	14	21
Week 4	22	28	42
Week 8	43	56	70
Week 12	71	84	126
Week 24	127	168	210
Week 36	211	252	294
Week 48	295	336	378
Week 60	379	420	462
Week 72	463	504	546
Week 84	547	588	630
Week 96	631	672	762

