- ¹⁸ If the scheduled visit coincides with the day that study drug administration is scheduled, the subject should be instructed not to administer the injection before coming to the site so that the assessments can be completed prior to study drug administration.
- ¹⁹ Additional NfL and CCI sample to be collected in case of any unscheduled visit due to suspected MS relapse

CCI CCI, CCI

- ²⁰ Assessment must be completed to allow adequate time for results to be obtained before first study drug administration to ensure subject's eligibility
- Women of childbearing potential only Serum pregnancy tests will be conducted on an annual basis at site. Monthly urine pregnancy tests will be conducted between scheduled visits at home and on scheduled visits (in the absence of an annual serum pregnancy test) at site prior to the administration of study drug. The subject must contact the Investigator immediately in the case of a positive test for confirmatory testing at the Investigator's discretion.
- ²² Subject's contraception status must be reviewed and documented to ensure method of contraception continues to be appropriate per protocol requirement for highly effective contraception.
- ²³ Including corticosteroids used to treat MS relapse; any new started MS treatment as applicable (for subjects who have discontinued study medications).
- ²⁴ Visit can be performed at the site or at subject's home with support of home nursing service. In this case an additional home nursing ICF must be signed.
- ²⁵ CCI and CCI should be given to the patient minimum 7 days prior to planned first study drug dose.
- To be assessed locally. If local testing is not feasible at a site, then these tests may be done by the Central Laboratory to assess patient's eligibility.
- ²⁷ MS relapses occurring after ICF signature should be assessed according to Section 8.3.1 and recorded on the Summary of MS Relapses eCRF.
- ²⁸ One additional medication kit can be dispensed at Visit 12/week 84, and taken by the subject prior to or no later than the day of the EOS visit, to ensure the subject does not have an interruption in treatment between study completion and start of commercial ofatumumab via prescription or via PTA mechanisms.

¹³ To be completed prior to first study drug administration

¹⁴ Patient Reported Outcomes: CCI

Table 8-2 Assessment Schedule, Safety Follow-up

Period		Po	st-Treatment Follow-up				

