2.1.2.3 Multiple assessments within visit windows

It is possible that multiple assessments of a participant fall into the same visit-window (e.g. due to unscheduled visits). All results (scheduled and unscheduled) will be displayed in listings, but only one value (observed or derived) will be selected for summary statistics by visit-window.

For quantitative variables, the assessment closest to the target day will be selected. If more than one assessment is at the same distance to the target day, the later one will be selected. For tables displaying the worst case scenario, such as shift tables or notable abnormalities, all assessments within a visit window will be used to identify the worst (e.g. the maximum or the minimum depending on parameter). Where applicable it will be defined for each parameter what the worst case is.

For qualitative variables, the worst record is selected; it is noted that in the relevant data subsection, worst case is always well defined.

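### SAP Table 2-3 opens the Week 24 window for T25FW and 9HPT on Day 1, so the pre-dose baseline value can stand as the Week 24 result when a subject has no later record in the window

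*SAP*

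**What the plan says.** **Mapping.** SAP 2.1.2.1: "For efficacy analyses all nominal visits (i.e. excluding unscheduled visits) will be mapped into one of the defined visit-windows". The next bullet maps all scheduled and unscheduled visits for safety analyses. SAP Table 2-1 counts every protocol-scheduled visit as nominal, including EOS.

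**Study day.** SAP 2.1.1: "For events with dates on or after Day 1, study day for the event is calculated as (event start date – first dose date + 1", with the bracket closing there. Only dates enter the formula, so any record on the first-dose date is Day 1.

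**Baseline.** SAP 2.1.1: "Baseline is the last assessment obtained prior to the first administration of study drug". SAP 2.1.2.1 adds: "Baseline assessments are defined in Section 2.1.1 and do not require a visit window".

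**Timing.** Protocol Table 8-1 schedules the office examinations (T25FW and 9HPT), PROs and C-SSRS at Visit 1, Day 1. Footnote 13 to that table reads: "To be completed prior to first study drug administration". T25FW, 9HPT and PROs have no earlier scheduled assessment.

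**First windows.** Table 2-3 (EDSS, T25FW, 9HPT): Week 24 is Days 1–252. Table 2-7 (B-cells, IgG, IgM, PROs): Week 4 is Days 1–98. Tables 2-6 and 2-9 (routine laboratory, biomarkers): Week 4 is Days 1–56. Table 2-10, "Visit-windows for eCSSRS": Week 2 is Days 1–21. Table 2-4 (MRI) starts Week 24 on Day 2. Table 2-5 (vital signs) starts on Day 1 but has a footnote: "Data collected from Day 1 protocol scheduled visit will not be mapped to the visit windows due to different data collection on this visit".

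**Choice within a window.** SAP 2.1.2.3 takes the quantitative value nearest the target day, with ties going to the later record. "For qualitative variables, the worst record is selected".

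**The concern.** The baseline record and the first post-baseline window share Day 1, and the mapping works on calendar day alone. The SAP says how baseline is identified. It does not say that the baseline record is then barred from the first post-baseline window. Two programmers could implement this differently, and one following the text literally would carry some baseline values forward.

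Where that happens, the by-visit table counts a subject who was not assessed after dosing, and that subject's change from baseline is zero by construction. The N is too large and the mean change is pulled towards zero.

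**Working it through.** There is no figure in the plan to reproduce. The check is day arithmetic on the SAP's own bounds.

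**Step 1: study day of a Visit 1 record.** First-dose date − first-dose date + 1 = Day 1.

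**Step 2: is Day 1 inside the first window, and when would it be selected?** The distance from target is |day − target|.

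| Table | Window (target) | Day 1 inside? | Distance of Day 1 | Later days in the window that lose to Day 1 |
|---|---|---|---|---|
| 2-3 T25FW/9HPT | 1–252 (168) | yes | 167 | none |
| 2-4 MRI | 2–252 (168) | no | – | – |
| 2-6 laboratory | 1–56 (28) | yes | 27 | 56 |
| 2-7 PROs, B-cells, Ig | 1–98 (28) | yes | 27 | 56–98 |
| 2-9 biomarkers | 1–56 (28) | yes | 27 | 56 |
| 2-10 eCSSRS | 1–21 (14) | yes | 13 | none |

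**Step 3: T25FW and 9HPT.** Day 2 is 166 days from target and Day 252 is 84, so every later record is nearer than Day 1. The baseline value is selected only when nothing else exists up to Day 252. SAP 2.14.9 summarises these tests by visit and, unlike the laboratory and vital-signs sections (2.9.3 and 2.9.4.2), does not restrict the table to subjects with a post-baseline value.

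**Step 4: PROs.** Day 55 is 27 days from target, a tie that the later record wins. Day 56 is 28 days away and loses. The Day 1 record therefore stands as Week 4 if there is no later record up to Day 98, or if the only later one falls on Days 56–98. SAP 2.12 places PRO analyses outside the CSR.

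**Step 5: laboratory, B-cell/Ig and biomarker samples.** Table 8-1 lets the Baseline visit run to Day 1 before dosing, although Protocol 8.1 says that Baseline and Day 1 should not share a day. Table 8-1 puts the first biomarker sample at Screening, but Protocol 8.5.2 refers to a biomarker sample before dosing at Visit 1. Any such sample drawn pre-dose on Day 1 meets the same problem.

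**Step 6: C-SSRS.** Under the worst-record rule, a positive pre-dose answer would become the Week 2 value whenever it is the worst in Days 1–21. The only summary specified (SAP 2.9.4.4) covers events at any time after baseline, and a pre-dose record is not after baseline.

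**Step 7: size for T25FW and 9HPT.** If a share p of the subjects in the Week 24 window are carried-in baselines, reported mean change = (1 − p) × mean change among those truly assessed. The documents give no value for p. For scale only, assumed values of 2%, 5% and 10% of 555 are 11, 28 and 56 subjects, and the mean shrinks by the same 2%, 5% and 10%.

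**The case against.** The best defence is that the SAP plainly intends baseline to be separate. Section 2.1.2.1 concerns the treatment epoch, and baseline is defined by timing relative to the first dose and is said to need no window. The mapping rule also cannot be fully literal: Screening is a nominal visit on negative days, and no window covers those. This is good evidence of intent, but it does not close the gap. Screening records drop out because no window contains them, whereas a Day 1 record does fall inside one.

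The contrast with the MRI and vital-signs tables is weaker than it looks. No MRI is scheduled on Day 1. The vital-signs footnote exists because pre- and post-injection values are both taken that day, and the pre-injection ones are not used for baseline. These tables show that Day 1 can be handled explicitly; they do not show that mapping it elsewhere was deliberate.

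The frequency argument also stands. Subjects who stop early are to have an EOS visit promptly, EOS includes the office examinations, and EOS counts as nominal. An early discontinuer should therefore usually have a later value in the window. The cases left are mainly Week 24 visits missed or held after Day 252, loss to follow-up, and withdrawal.

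A reader might infer that pre-dose suicidality findings will be reported as on-drug findings, or that PRO tables in the CSR will be distorted. The documents support neither: no by-window C-SSRS table is specified, and PROs are not in the CSR.

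**Conclusion.** The gap is real and its effect is small. As written, the pre-dose T25FW or 9HPT value becomes the Week 24 value, with zero change, for any subject with no later record up to Day 252. The same wording reaches PROs at Week 4 (outside the CSR) and any laboratory, B-cell/Ig or biomarker sample drawn pre-dose on Day 1. C-SSRS is at risk only if a by-window table is produced.

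This is a rule whose literal application gives a wrong result. It does not show that subjects will be misclassified, since a programmer may well drop baseline records anyway. The number affected cannot be derived from the documents; the 2–10% range is an assumption, and the EOS requirement limits the number. Only exploratory or descriptive by-visit summaries are touched. The primary ARR analysis uses relapse counts and time in study, not these windows. 6mCDW uses all EDSS visits rather than one value per window.

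**What to change.** Add one sentence to SAP 2.1.2.1: *Assessments taken before the first administration of study drug, including pre-dose Day 1 assessments, are not mapped to post-baseline visit windows.* Also start the Week 24 window in Table 2-3 on Day 2, as Table 2-4 already does.

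Leave the Day 1 start in the safety tables. A Day 2 start there would leave genuine post-dose Day 1 safety records without a window, although the SAP maps all safety visits.

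The cost is one sentence and one digit. There is no change to data collection, design or the primary analysis. Footnote 13 makes the Visit 1 office examinations, PROs and C-SSRS pre-dose by design, so the visit label is enough to identify them. If the programs already exclude baseline records, no result changes.
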